#### **6.3.2. Biomarkers**

Absolute and changes from baseline in blood hs-CRP, LDH, Ferritin, WBC, Monocytes, Haptoglobin, Procalcitonin, Neutrophils and Creatine Kinase will be summarized by treatment and time post-dose. Baseline is as defined in [Section 3.3.2](#).

Absolute and changes from baseline in coagulation markers (D-dimer, PT, aPTT) and Fibrinogen will be summarized by treatment and time post-dose. Baseline is as defined in [Section 3.3.2](#).

Absolute and changes from baseline in cytokines of inflammatory response will be summarized by treatment and time post-dose. Baseline is as defined in [Section 3.3.2](#).

Individual and mean changes from baseline plots will be produced by treatment. For cytokines - individual absolute plots will also be produced.

The percentage of participants with Reactive and Non-Reactive IgG will be summarized by treatment.

Listings of biomarkers, coagulation markers, cytokines and serology will be produced separately to the laboratory listing.

CCI

A series of black redaction bars of varying lengths, starting with a short one under 'CCI' and continuing with longer ones below it, ending with a very long one at the bottom.

#### **6.4. Subset Analyses**

No subset analyses will be performed.

#### **6.5. Baseline and Other Summaries and Analyses**

##### **6.5.1. Study Conduct and Participant Disposition**

Participant evaluation groups will show participant disposition for each phase of the study (screening, treatment and follow-up) and will additionally show which participants were analysed for PK, biomarker as well as for safety. Frequency counts and percentages will be supplied for participant discontinuation(s) by treatment. Data will be reported in accordance with the sponsor reporting standards.

### **6.5.2. Demographic Data**

Demographic data (age, gender, race, ethnicity, weight, body mass index and height) will be summarised by treatment and overall (if applicable) in accordance with the sponsor reporting standards.

### **6.5.3. Significant Medical History**

Significant medical history will be summarized by treatment and overall.

### **6.5.4. Study Treatment Exposure**

For **Part 2: MAD**, a summary table of infusion duration will be presented by treatment and overall

### **6.5.5. Concomitant Medications and Nondrug Treatments**

All prior and concomitant medication(s) as well as non-drug treatment(s) will be reported according to current sponsor reporting standards.

## **6.6. Safety Summaries and Analyses**

See [Section 6.1](#) for details.

## **7. INTERIM ANALYSES**

### **7.1. Introduction**

*No formal interim analysis will be conducted for this study. However, as this is a sponsor-open study, the sponsor will conduct unblinded reviews of the safety and PK data during the course of the study along with the IRC for the purpose of safety assessment, facilitating dose-escalation decisions, facilitating PK/PD modeling, and/or supporting clinical development. Unblinded results will be reviewed by a designated limited number of sponsor colleagues within the study team.*

*An independent IRC will assess whether it is safe to proceed to continued dosing after a small sentinel cohort of 2 participants within each dose-escalating cohort or if it is safe to dose-escalate to the next dose level within Part 1.*

### **7.2. Interim Analyses and Summaries**

N/A

## APPENDICES

### Appendix 1. Categorical Classes for ECG and Vital Signs of Potential Clinical Concern

#### Categories for QTcF

|                                       |                     |                     |      |
|---------------------------------------|---------------------|---------------------|------|
| Absolute value of QTcF (msec)         | >450 and $\leq$ 480 | >480 and $\leq$ 500 | >500 |
| Increase from baseline in QTcF (msec) | >30 and $\leq$ 60   | >60                 |      |

#### Categories for PR and QRS

|                                 |   |  |
|---------------------------------|---|--|
| PR (ms)                         | max. $\geq$ 300                               |  |
| PR (ms) increase from baseline  | Baseline $>$ 200 and max. $\geq$ 25% increase | Baseline $\leq$ 200 and max. $\geq$ 50% increase |
| QRS (ms)                        | max. $\geq$ 140                               |  |
| QRS (ms) increase from baseline | $\geq$ 50% increase                           |  |

#### Categories for Vital Signs & Pulse Oximetry

|   |                         |                         |
|---|-------------------------|-------------------------|
| Systolic BP (mm Hg)                       | min. $<$ 90             |                         |
| Systolic BP (mm Hg) change from baseline  | max. decrease $\geq$ 30 | max. increase $\geq$ 30 |
| Diastolic BP (mm Hg)                      | min. $<$ 50             |                         |
| Diastolic BP (mm Hg) change from baseline | max. decrease $\geq$ 20 | max. increase $\geq$ 20 |
| Supine pulse rate (bpm)                   | min. $<$ 40             | max. $>$ 120            |
| Standing pulse rate (bpm)                 | min. $<$ 40             | max. $>$ 140            |
| Pulse oximetry/SpO2 (%)                   | $<$ 94                  |                         |

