### **3.1.2. Laboratory Data**

Safety laboratory tests will be performed as described in the protocol.

Baseline will be the last pre-dose measurement.

To determine if there are any clinically significant laboratory abnormalities, the haematological, clinical chemistry (serum) and urinalysis safety tests will be assessed against the criteria specified in the sponsor reporting standards. The assessment will take into account whether each participant's baseline test result is within or outside the laboratory reference range for the particular laboratory parameter.

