### **3.1.5. Pulse Oximetry/SpO2**

Pulse oximetry/SpO2 will be taken at times detailed in the SoA given in the protocol.

The following pulse oximetry endpoints will be determined:

- Change from baseline in pulse oximetry/SpO2

Baseline will be defined as the last pre-dose measurement.

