#### **6.1.5. Pulse Oximetry/SpO2**

Absolute values and changes from baseline in pulse oximetry/SpO2 will be summarized by treatment and time post-dose. Baseline is as defined in [Section 3.1.5](#).

Numbers and percentages of participants meeting the categorical criteria as defined in [Appendix 1](#) will be provided. All planned and unplanned post-dose timepoints will be counted in these categorical summaries.

All tables above will have three columns per treatment based on whether the participant is receiving oxygen CCI throughout, at somepoint during the study or never received. Days 2 to 6 will be used i.e. Days 2, 3 & 6 for Part 1: SAD and Days 2, 3, 4, 5 & 6 for Part 2: MAD and any unplanned readings between Day 2 and Day 6 will be used (where collected).

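### The supplementary SpO2 below-94% count does not separate participants already below 94% before dosing from those who fall below it afterwards

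*SAP*

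**What the plan says.** SAP Appendix 1 has one row for "Pulse oximetry/SpO2", with a single absolute limit of below 94%. For the categorical table SAP 6.1.5 states: "All planned and unplanned post-dose timepoints will be counted in these categorical summaries". No condition on the pre-dose value appears in either place. SAP 3.1.5 does define a baseline ("Baseline will be defined as the last pre-dose measurement") and makes change from baseline the SpO2 endpoint, in line with the primary endpoints in Protocol section 3. SAP 6.1.5 summarises absolute values and changes by treatment and time.

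The SpO2 tables are also divided by oxygen use: "All tables above will have three columns per treatment based on whether the participant is receiving oxygen" throughout, at some point or never. The period for that classification follows: "Days 2 to 6 will be used i.e. Days 2, 3 & 6 for Part 1: SAD", with Days 2 to 6 for Part 2.

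Other safety measures use baseline in their flags or summaries:
- Laboratory abnormalities (SAP 3.1.2) take account of whether the "baseline test result is within or outside the laboratory reference range for the particular laboratory parameter".
- Blood pressure has change rows in Appendix 1, for example "Systolic BP (mm Hg) change from baseline". QTcF and QRS have increase rows, and the PR increase category depends on the baseline value.
- SAP 3.1.3 defines a maximum decrease or increase from baseline for blood pressure, respiratory rate, pulse rate and temperature. SAP 3.1.5 defines none for SpO2.

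**The concern.** The trial enrols hospitalised patients with mild, moderate or severe COVID-19 (Protocol 4.1). The visible exclusions stop at ventilation, ECMO and respiratory failure (Protocol 5.2) and set no SpO2 floor. Some participants may therefore start below 94%.

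A participant who enters at 92% and stays at 92% is counted exactly like one who falls from 98% to 92%. Only the second has shown anything after dosing. A reader would naturally take the table as a measure of desaturation on treatment, but part of it may be a measure of severity at entry. With 6 active and 2 placebo participants per cohort, a chance difference in entry severity can then look like a treatment difference, or hide one.

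**Working it through.** The plan states no figure on this point and makes no formal sample size calculation (Protocol 9.2), so there is nothing to reproduce. The first step is a reading of the text; the other two are illustrations.

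**Step 1. Can any planned SpO2 output tell a new low value from an old one?**

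| Output (SAP 6.1.5) | Uses baseline SpO2? | Shows whether a participant's low value is new? |
|---|---|---|
| Below-94% count | No | No |
| Absolute value by time | Group level only | No |
| Change from baseline by time | Yes | No: group statistics at each time, not each participant's worst change |
| Oxygen-use columns | No: oxygen use on Days 2 to 6 | No |

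SAP 6.4 plans no subset analyses, so no table by baseline SpO2 arises elsewhere.

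**Step 2. How much of the count could be old?** Let b be the share below 94% at baseline, s the share of these with at least one post-dose reading below 94%, and d the share of the others who become low after dosing. None of these is in the documents. Assumed ranges: b 0.1 to 0.5, s 0.7 to 0.9, d 0.1 to 0.2.

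- Share of participants counted = b·s + (1 − b)·d
- Part of the count already low at entry = b·s / [b·s + (1 − b)·d]

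| b | s | d | Share counted | Already low at entry |
|---|---|---|---|---|
| 0.1 | 0.7 | 0.2 | 0.07 + 0.18 = 0.25 | 0.07/0.25 = 28% |
| 0.3 | 0.9 | 0.1 | 0.27 + 0.07 = 0.34 | 0.27/0.34 = 79% |
| 0.5 | 0.9 | 0.1 | 0.45 + 0.05 = 0.50 | 0.45/0.50 = 90% |

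The first and last rows are the extremes of the assumed range. In the middle row the planned count gives 34%, while the rate among those at or above 94% at baseline is 10%.

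**Step 3. Chance imbalance at entry.** Let x of 6 active and y of n placebo participants be low at baseline, both binomial with the same rate b. The probability that the two shares differ by at least one third is the sum of P(x)·P(y) over all pairs with |x/6 − y/n| ≥ 1/3. For b = 0.5 and n = 2 it is (1/4)(57/64) + (1/2)(14/64) + (1/4)(57/64) = 35.5/64 = 0.555.

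| b | n = 2 (one Part 1 cohort) | n = 8 (placebo pooled over four Part 2 cohorts) |
|---|---|---|
| 0.1 | 0.262 | 0.077 |
| 0.2 | 0.471 | 0.172 |
| 0.3 | 0.554 | 0.225 |
| 0.5 | 0.555 | 0.238 |

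The n = 2 column is high partly because a share out of two can only be 0, 50% or 100%. These are imbalances at entry. They reach the table only for participants who also have a low reading after dosing.

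**The case against.** The strongest reply is that the baseline-adjusted analysis already exists. A reader might infer from the Appendix 1 row that the primary SpO2 endpoint ignores baseline. The documents do not support that: the endpoint is change from baseline, and it is tabulated. The below-94% count is an additional flag. This objection stands and limits the point to a supplementary table.

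The oxygen columns are a second partial answer, since they sort participants roughly by severity. But they rest on oxygen use after the infusion has started, which disease course or treatment can affect, and they divide groups of 6 and 2 still further.

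Third, entry levels are visible at group level. SAP 5.2 includes screening in the summaries, and SAP 5.2.1 gives minimum and maximum. This shows whether a group contained low entrants, but not whether the participants counted later are the same people.

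A reader might also infer that everyone low at entry is counted. Not so: only post-dose readings count, so someone who recovers to 94% or above is left out. Nor should one set the chance that at least 1 of 6 active participants is low at entry (74% to 98% for rates of 20% to 50%) against at least 1 of 2 on placebo (36% to 75%) as evidence of bias. Those figures assume a rate with no source and full persistence. They differ because the groups differ in size, whereas the expected percentages are equal under randomisation.

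Absolute-only limits are not peculiar to SpO2. Pulse rate has them too in Appendix 1, but SAP 6.1.3 adds a maximum increase for pulse rate. Adverse event reporting is a further route to new desaturation, though Protocol Appendix 3 leaves out findings associated with the underlying disease unless they are more severe than expected. Separate placebo reporting by cohort is stated for Part 1 only; for Part 2 the SAP specifies pooled placebo in the vital-sign and ECG plots.

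**Conclusion.** The point holds for the supplementary table only. As written, the count does not exclude or separate participants whose last pre-dose SpO2 was below 94%, so it can mix entry severity with desaturation after dosing, and no other planned SpO2 output resolves this for each participant. That conclusion rests on the text alone.

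The size is unknown. The documents give no frequency of low SpO2 at entry, and inclusion criterion 5, which could bear on it, is blacked out. The 28% to 90% range and the imbalance probabilities are illustrations under the stated assumptions, not estimates for this trial. If few participants enter below 94%, the effect is small.

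The analysis is descriptive, with no hypothesis tests or statistical decision rules (SAP 5.1), and the stopping rules in Protocol 6.6.1 do not refer to this count. What is at stake is the interpretation of one safety table. The change is a cheap improvement.

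**What to change.** In SAP 6.1.5 and Appendix 1, keep the existing count and add:

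1. a shift table by treatment, with baseline SpO2 (below 94%, or at or above 94%) against the lowest post-dose SpO2 in the same two categories;
2. the number and percentage with any post-dose value below 94% among participants at or above 94% at baseline, with that denominator shown;
3. the maximum decrease from baseline in SpO2 over all planned and unplanned post-dose readings, defined in SAP 3.1.5 with the convention that SAP 3.1.3 already uses for blood pressure and respiratory rate.

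The data are already scheduled: both Schedules of Activities include SpO2 at screening, before dosing and after dosing. The cost is one extra table and one extra summary. Cells will be small, so the shift table should show counts and is best given without the oxygen columns. No change to design, data collection or clinical conduct is needed.
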